	8.8.3. Point prevalence	
	8.8.4. Incidence rates	19
	8.8.5. Median disease duration	19
	8.8.6. Indirect estimated prevalence	19
8.	.9 Evidence synthesis	20
9	DATA MANAGEMENT	20
10	QUALITY CONTROL	21
11	LIMITATIONS OF THE RESEARCH METHODS	21
12	MANAGEMENT AND REPORTING OF ADVERSE EVENTS/ADVERSE REACTIONS	22
13	GOVERNANCE BOARD ASPECTS	
14	PLANS FOR DISSEMINATING AND COMMUNICATING STUDY RESULTS	22
15	OTHER ASPECTS	
16	REFERENCES	22
17	ANNEXES	23

DOCUMENT HISTORY

VERSION	DATE	DESCRIPTION	
1.0	19/01/2024	First draft	
1.1	14/02/2024	Updated version for archiving purposes	
1.2	02/04/2024	Updated version for archiving purposes	
2.0	12/07/2024	Final version uploaded in the HMA-EMA Catalogue	

Version: 2.0

Dissemination level: Public

Study Title	DARWIN EU [®] - Comparing direct and indirect methods to estimate		
	prevalence of chronic diseases using real-world data.		
Protocol version identifier	2.0		
Date of last version of protocol	12/07/2024		
EU PAS register number	EUPAS100000088		
Active substance	NA		
Medicinal product	NA		
and objectives	In the context of chronic diseases with relatively low prevalence, how do direct and indirect RWD-based estimates of prevalence compare with each other? The specific objectives of this study are to: 1) Estimate the disease prevalence (direct estimate based on the proportion of individuals with the condition). 2) Estimate the disease incidence rate. 3) Estimate duration of disease using Kaplan-Meier survival curves. Of particular interest is the estimate of median survival as a summary measure of disease duration. 4) Produce an indirect estimation of prevalence as the product of incidence and median survival. for the following diseases: • Cystic fibrosis • Haemophilia (A and/or B) • Pulmonary arterial hypertension • Pancreatic cancer • Sickle cell disease Results will be provided overall and where possible stratified by age group: paediatrics (0-17 years old) and adults (18 years old and above).		
Country(ies) of study	United Kingdom, the Netherlands, Spain		
Author	[name]		

LIST OF ABBREVIATIONS

Acronyms/terms	Description		
CDM	Common Data Model		
CI	Confidence Interval		
CPRD GOLD	Clinical Practice Research Datalink GOLD		
DARWIN EU®	Data Analysis and Real-World Interrogation Network		
EHR	Electronic Health Records		
EMA	European Medicines Agency		
GP	General Practitioner		
IP	Inpatient		
IPCI	Integrated Primary Care Information Project		
NA	Not applicable		
NL	the Netherlands		
ОМОР	Observational Medical Outcomes Partnership		
OP	Outpatient		
RWD	Real-World Data		
SIDIAP	Sistema d'Informació per al Desenvolupament de la Investigació en Atenció Primària		
SP	Spain		
ТВС	To be confirmed		
UK	United Kingdom		

3. ABSTRACT (STAND ALONE SUMMARY OF THE STUDY PROTOCOL)

Title

DARWIN EU® - Comparing direct and indirect methods to estimate prevalence of chronic diseases using real-world data

Rationale and background

Prevalence of a disease or condition is defined as the proportion of individuals in a population affected by a condition at a given point in time. Quantifying disease prevalence is important from a public health perspective, e.g. to understand the impact of diseases on the population, or to plan and allocate health care resources. Measuring disease prevalence is also important from a medicine regulatory viewpoint, as regulatory agencies grant incentives for the development of new therapies for rare diseases, i.e. diseases with low prevalence.

Disease prevalence depends on the rate of incidence of the disease in the population as well as on the average duration of the disease. Under the assumption that both the incidence of the disease and its average duration are stable over time, a well-known mathematical relationship between prevalence (P), incidence (I) and average duration (D) is:

$$\frac{P}{1-P} = I \cdot D$$

When P is low, $(1 - P) \approx 1$ and the equation reduces to the following expression for the indirect estimated prevalence:

$$P = I \cdot D$$

In this study direct and indirect estimated prevalence will be compared using real-world data sources.

Research question and objective

The objective of this study is to compare direct and indirect estimations of prevalence of some rare, chronic diseases.

This will be done considering all patients with the disease as well as separately for patients with paediatric diagnosis (age 0-17 years) and for patients with adult diagnosis (age 18 and older).

Research Methods

Study design

A retrospective cohort design to estimate disease point prevalence and incidence.

A retrospective cohort design to estimate median survival as a proxy for disease duration. Data from three databases with routinely-collected electronic healthcare records of general practices will be used.

Population

All individuals present in one of the databases during the study period 01/01/2010 to 31/12/2022 will be used to estimate incidence and prevalence.

All patients with the disease will be used to estimate median disease duration.

Variables

Presence of a diagnosis of

- Cystic fibrosis
- Haemophilia
- Pulmonary arterial hypertension
- Pancreatic cancer
- Sickle cell disease

Age at first diagnosis.

Time from first diagnosis to death.

Data sources

- 1. Integrated Primary Care Information Project (IPCI), The Netherlands
- 2. Sistema d'Informació per al Desenvolupament de la Investigació en Atenció Primària (SIDIAP), Spain
- 3. Clinical Practice Research Datalink GOLD (CPRD GOLD), United Kingdom

Sample size

No sample size has been calculated. All patients with the disease will be included.

Data analyses

Population-level disease epidemiology: for each disease of interest, the complete point prevalence at the middle of the study period, i.e. 01/01/2016, will be calculated as well as incidence rate over the total study period.

For each patient only the first diagnosis of a disease will be considered. The date of this diagnosis can be before the observation period of the patient, i.e. before the period during which the patient is monitored in the database. A GP can have entered historical events, for example the diagnosis of an inherited disease. Also, information received from a patient's former GP might be imported. For this study, it is important to have as much patient's history as possible. The disease is considered to stay present during patient's observation period (and beyond). For point prevalence, all persons with a diagnosis before 01/01/2016 and in observation in the database at this date contribute to the numerator. The denominator is the total number of persons in observation on 01/01/2016. For the calculation of the incidence rate, only newly diagnosed patients (diagnosed within the observation time and within the study period) contribute to the numerator. The denominator is the total number of person-years at risk, i.e. the sum across all subjects included in the cohort of the observation time within the study period or until a diagnosis occurs.

Survival estimation: Kaplan Meier estimates for survival probabilities for time since first diagnosis. Median survival, as a proxy for disease duration, is the time point where the survival probability decreases to below 50%.

For all analyses a minimum cell count of 5 will be used when reporting results, with any smaller counts reported as "<5". Counts of zero will be reported.

From the incidence rate and median disease duration, the indirect prevalence will be calculated.

Results from the databases will be combined using random effects meta-analysis.

4. AMENDMENTS AND UPDATES

NUMBER	DATE	SECTION OF STUDY PROTOCOL	AMENDMENT OR UPDATE	REASON
None				

5. MILESTONES

STUDY SPECIFIC DELIVERABLE	TIMELINE
Draft Study Protocol	18/01/2024
Final Study Protocol	02/04/2024
Creation of Analytical code	19/02/2024
Execution of Analytical Code on the data	26/02/2024
Interim Study Report (if applicable)	NA
Draft Study Report	28/03/2024
Final Study Report	22/04/2024

6. RATIONALE AND BACKGROUND

Prevalence of a disease or condition is defined as the proportion of individuals in a population affected by a condition at a given point in time. Quantifying disease prevalence is important from a public health perspective, e.g. to understand the impact of diseases on the population, or to plan and allocate health care resources. Measuring disease prevalence is also important from a medicine regulatory viewpoint, as regulatory agencies grant incentives for the development of new therapies for rare diseases, diseases with low prevalence.

If the number of people with the disease is known in a population of known size, direct estimation of the prevalence proportion is straightforward. This holds for a sample of the population, provided the sample is representative of the population. For chronic diseases, complete prevalence, i.e. counting all individuals ever diagnosed with the disease, is typically of interest.

Disease prevalence depends on the rate of incidence of the disease in the population as well as on the average duration of the disease. Under the assumption that both the incidence of the disease and its average duration are stable over time, a well-known mathematical relationship between prevalence (P), incidence (I) and average duration (D) is[1]:

$$\frac{P}{1-P} = I \cdot D$$

For diseases with relatively low prevalence, $(1 - P) \approx 1$ and the above expression reduces to:

 $P = I \cdot D$

Application of this formula can be useful for example when the prevalence is unknown but where the incidence can be estimated from diagnoses in hospitals, and using assumptions for the duration of disease [2], or where input from different sources is combined [3].

This expression can be used to obtain an indirect estimation of disease prevalence from estimates of the disease incidence and mean (or median) duration, provided the following assumptions hold:

- The prevalence is relatively low
- Disease incidence is stable over time
- Disease duration is stable over time

For chronic diseases without cure, the value of D used can correspond to the median survival time after diagnosis. For non-chronic diseases, the value of D used can correspond to the median time from diagnosis to cure.

In recent years, real-world data (RWD) sources, particularly from primary care, have been used to estimate the prevalence of chronic diseases. The rationale behind this is that the population included in these databases can be considered a representative sample of the general population. The same reasoning has been used to produce incidence figures as well as estimations of disease duration (e.g. survival) using this type of sources.

There is uncertainty however around how direct and indirect methods to estimate prevalence agree with each other, both in situations where the assumptions underpinning the indirect method hold, the degree to which a chronic disease is truly life-long, as well as in settings where they can be more questionable (e.g. because incidence and or disease duration evolved over time). This study aims at addressing this question in the context of using RWD sources.

7. RESEARCH QUESTION AND OBJECTIVES

Table 1 shows the objective of this study with some specifications.

Table 1. Primary and secondary research questions and objective.

Objective:	To compare direct and indirect estimations of prevalence of some rare, chronic diseases
Hypothesis:	No hypothesis is tested
Population:	Total population in the databases
Diseases: Cystic fibrosis Haemophilia (A and/or B) Pulmonary arterial hypertension Pancreatic cancer Sickle cell disease	
Setting:	3 databases with Electronic Healthcare Records from primary care
Main outcome:	Direct and indirect estimated prevalences

A. Primary research question and objective.

8. **RESEARCH METHODS**

8.1 Study type and Study Design

Table 2 shows the study types and designs for this study, both for the population-level analyses (incidence and prevalence) and the patient-level analyses (disease duration in patients diagnosed).

Table 2. Description of Potential Study Types and Related Study Designs.

STUDY TYPE	STUDY DESIGN	STUDY CLASSIFICATION
Population-level descriptive epidemiology	Population-level cohort	Off the shelf
Patient-level characterisation	Cohort analysis	Off the shelf

Incidence rate and complete point prevalence will be estimated in the total population of the databases.

Disease duration (approximated with the median survival time from first diagnosis until death) will be estimated in patients with the disease.

8.2 Study Setting and Data Sources

For this study, suitable data sources should include individuals who can be considered as a representative sample of the general population and have the potential for long observation periods for subjects. Therefore, we focus on primary care data sources and hospital data sources are not included. Lifelong observation of patients is not available in any of the data sources within the DARWIN EU network, however, patients in primary care databases will often have several years of observation time. Also history of diagnoses before subject's observation time might be recorded. In addition, data sources should have a good recording of mortality.

When it comes to assessing the reliability of data sources, the data partners were asked to describe their internal data quality process on the source data as part of the onboarding procedure. In addition, they are asked to share the results from three data quality assurance package: CdmOnboarding, Data Quality Dashboard (DQD) and DashboardExport. The latter exports a subset of analyses from the Achilles tool (https://github.com/OHDSI/Achilles), which systematically characterizes the data and presents it in a dashboard format to ease the detection of potential quality issues. The generated data characteristics such as age distribution, condition prevalence per year, data density, measurement value distribution can be compared against the national healthcare data. CdmOnboarding creates a report with select characterisation of the clinical data within the database and details on mapping coverage statistics that are closely inspected upon onboarding. DQD provides more objective checks on conformance and plausibility, applied consistently across the data sources.

For eligible data sources within the DARWIN EU network, counts of initially suggested diseases were produced. This resulted in selecting the three primary care databases presented in Table 3.

	D2.2.3 - Study Protocol for P2-C1-013	
EUM	Author(s): [name], [name]	Version: 2.0
		Dissemination level: Public

Table 3. Description of the selected Data Sources.

Country	Name of Database	Justification for Inclusion	Health Care setting	Type of Data	Number of active subjects	Feasibility count of disease (if relevant)	Data lock for the last update
United Kingdom	CPRD GOLD	Sufficient feasibility counts, sufficiently long median duration of observation periods, good recording of mortality	Primary care	EHR	3.0 million		Source data 01/07/2023
the Netherlands	IPCI	Sufficient feasibility counts, sufficiently long median duration of observation periods, good recording of mortality	Primary care	EHR	1.3 million		Source data 23/09/2023
Spain	SIDIAP	Sufficient feasibility counts, sufficiently long median duration of observation periods, good recording of mortality	Primary care	EHR	5.8 million		Source data 30/06/2023

Study Period

Study period is from January 1st, 2010, to December 31st, 2022.

8.3 Follow-up

For all individuals in the databases, the observation period is recorded, i.e. the period during which the individual is monitored. In the primary care databases used in this study, it is the period the individual is registered in the GP practice.

• For the incidence estimation, the follow-up is the part of patient's observation period that overlaps with the study period. Only first diagnoses which fall within this follow-up period will contribute to

the incidence numerator. The follow-up period will contribute time at risk to the person-years denominator, restricted to the time before the first diagnosis of the relevant disease, if present.

- For the direct estimation of the point prevalence, a disease diagnosed before an individual's observation period, if present, will also be captured. Diagnoses before the observation period can be present if a GP has received information about the patient's history from the former GP, or if a GP enters historical information, e.g. the diagnosis date of an inherited disease. However, individuals can only contribute to the point prevalence numerator and denominator if the time point used to assess the point prevalence is within their observation period.
- In the survival analysis, the follow-up of patients starts at the first diagnosis of the disease of interest and ends at patient's death, end of patient's observation period or end of the study period, whatever comes first.

Further information on follow-up time is given in Table 4.

	D2.2.3 - Study Protocol for P2-C1-013			
EUM	Author(s): [name], [name]	Version: 2.0		
		Dissemination level: Public		

Table 4. Operational Definition of Time 0 (index date) and other primary time anchors.

Study population name(s)	Time Anchor Description	Number of entries	Type of entry	Washout window	Care Setting ¹	Code Type ²	Incident with respect to
Total population	Start of FU: latest of: - entry in database - start of study period (01/01/2010) End of FU: earliest of: - date of mortality - end of patient's observation period, i.e. deregistration of patient or end of GP data contribution - end of study period (31/12/2022)	1	NA	NA	PC, IP and OP	NA	NA
Patients with disease diagnosis	Start of FU: first diagnosis of disease End of FU: earliest of: - date of mortality - end of patient's observation period, i.e. deregistration pf patient or end of GP data contribution - end of study period (31/12/2022)	1	Incident	[-Inf, -1]	PC, IP and OP	SNOMED codes	Disease of interest

¹IP = inpatient, OP = outpatient, NA = not applicable, PC = primary care

Dissemination level: Public

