8.4 Study Population with inclusion and exclusion criteria

For the incidence and prevalence estimations, the complete database population will be included.

For disease duration, all patients with the diagnosis of interest will be included, without any exclusion criteria.

Inclusion criteria are described in Table 5.

Criterion	Details	Assessment window	Care Settings ¹	Code Type	Applied to study populations:
Patients with a disease diagnosis	Earliest recording of disease diagnosis will be identified, this can be before or during observation time	Complete history and observation period of patient	PC, IP and OP	SNOMED code	Patients with disease diagnosis
Pediatric patients	Earliest recording of disease is at age 0-17	Complete history and observation period of patient	PC, IP and OP	SNOMED code	Patients with disease diagnosis at paediatric age
Adult patients	Earliest recording of disease is at age 18+	Complete history and observation period of patient	PC, IP and OP	SNOMED code	Patients with disease diagnosis at adult age

¹IP = inpatient, OP = outpatient, NA = not applicable, PC = primary care

No exclusion criteria are applied

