8.8.5. Median disease duration

Survival time will be analysed with the R package *survival*. Time zero for the survival analysis is the date of first diagnosis. Patients for whom no date of death is recorded will be censored at the date of end of their observation period or administratively censored at the end of study period.

Median survival time, i.e. disease duration, will be estimated with 95% CI using Brookmeyer-Crowley method [4].

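### Survival is counted from a first diagnosis that may precede database entry, with no delayed entry, so the median duration D is biased upward by an amount that depends on how many historical diagnoses are recorded

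*Protocol*

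**What the plan says.** The protocol fixes who enters the duration analysis and when their clock starts.

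- **Who enters.** Section 8.4: "For disease duration, all patients with the diagnosis of interest will be included, without any exclusion criteria". Table 5 adds: "Earliest recording of disease diagnosis will be identified, this can be before or during observation time". The abstract (section 3) agrees: "The date of this diagnosis can be before the observation period of the patient, i.e. before the period during which the patient is monitored".
- **When the clock starts.** Section 8.3: "In the survival analysis, the follow-up of patients starts at the first diagnosis of the disease of interest and ends at" the earliest of death, end of observation and end of study. Section 8.8.5: "Time zero for the survival analysis is the date of first diagnosis". The disease row of Table 4 reads: "Start of FU: first diagnosis of disease End of FU: earliest of: - date of mortality - end of patient's observation period". The total-population row of the same table is built differently: "Start of FU: latest of: - entry in database - start of study period (01/01/2010".
- **What is corrected.** Section 8.8.5 describes censoring at the end of observation or at the end of the study. Delayed entry, left truncation and restriction to diagnoses made under observation are not mentioned anywhere.
- **Where D goes.** Section 8.8.6 multiplies the incidence I by the median D. Sections 8.3 and 8.8.4 count only diagnoses made within observation towards I.

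**The concern.** Someone diagnosed before registering with a contributing practice can appear in the database only if still alive at registration. People with the same diagnosis date who died sooner are never seen. Starting the survivor's clock at diagnosis credits years in which a death could not have been observed. The early risk sets are too large, the estimated hazard is too low and the median is too long. This happens even when every recorded date is correct.

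The direct prevalence in section 8.8.3 counts people under observation on a given date and has no such bias. The study's only objective is to compare the two estimates, so an artefact in D could be reported as a property of the indirect method. Exposure to it is greatest for long-lasting inherited diseases, which are the protocol's own example of where historical dates are entered.

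This is not detail left to an analysis plan. The start of follow-up is stated in the text of 8.3, in Table 4 and in 8.8.5, and a programmer following any of them would code the biased version.

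**Working it through.** **No figure to reproduce.** The protocol gives no incidence, median, event count or share of historical diagnoses. The size below therefore comes from simulation on stated assumptions.

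**Formula.** For patient i, on the scale of time since diagnosis:

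- exit = min(death, end of observation, 31/12/2022) − diagnosis date
- entry = max(0, start of observation − diagnosis date)
- Kaplan-Meier: S(t) = ∏(1 − d_j/n_j) over death times t_j ≤ t

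As written, n_j counts everyone with exit ≥ t_j. It should count only those with entry < t_j ≤ exit.

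**Illustration (invented dates).** Diagnosis in 2000, registration in 2012, censoring in 2020. The plan counts 2020 − 2000 = 20 years at risk. Death could be observed only from year 12 to year 20, which is 8 years.

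**Simulation inputs (assumptions, not from the protocol).** Constant incidence over 90 years; a registration spell around a random date in 2010–2022; 7% per year practice turnover; data from 1995; end of study 2022; inclusion if alive at registration. Survival is exponential, except Weibull shape 0.6 for the 0.5-year median and shape 2 for the 30-year median. Pre-registration diagnoses that are not recorded are dropped.

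Ratio of the median under the plan's rule to the true median, by share of pre-registration diagnoses recorded:

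| True median | 10% | 25% | 50% | 100% |
|---|---|---|---|---|
| 0.5 y | 1.02 | 1.05 | 1.10 | 0.60/0.5 = 1.20 |
| 3 y | 1.03 | 1.07 | 1.14 | 3.8/3 = 1.27 |
| 5 y | 1.05 | 1.13 | 1.25 | 7.3/5 = 1.46 |
| 15 y | 1.27 | 1.60 | 1.96 | 33.5/15 = 2.23 |
| 30 y | about 1.3 | | | 42/30 = 1.40 |

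At 100% recorded, delayed entry returns 0.50, 3.0, 5.0, 15.0 and 29.8 years.

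**Sensitivity to the registration pattern.** With registration starts uniform over 1990–2022, a mean spell of 8 years and exponential survival, 10% to 100% recorded gives ratios of 1.01–1.09 (0.5 y), 1.10–1.72 (3 y) and 1.76–3.41 (10 y). At a true 40 years the plan's rule reaches no median in most runs. Delayed entry returned 0.50, 3.00–3.02 and 9.92–10.09 years, and 38.6–41.7 years for a true 40. The direction and the remedy do not change; the factor does.

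**Effect on P.** I is not touched by this error, so I·D is inflated by the same ratio relative to I × true median. The steady-state prevalence is I × mean duration, which is a different reference. For exponential survival the median is ln 2 = 0.69 of the mean. With everything recorded, the plan's median over the true mean is:

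- 15 y: 33.5/(15/0.693) = 33.5/21.6 = 1.55
- 5 y: 7.3/7.21 = 1.01
- 3 y: 3.8/4.33 = 0.88
- 30 y, shape 2: 1.32
- 0.5 y, shape 0.6: 0.43

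With D corrected and the median still used, the same ratios are 0.69, 0.69, 0.69, 0.94 and 0.36.

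**Entry at 01/01/2010.** If the disease cohort is limited to people present in 2010–2022, patients must also have survived to 2010. Delayed entry at registration alone then gave 22 years for a true 15. Adding 01/01/2010 to the entry rule restored 15.

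**The case against.** **Incidence label and washout.** Table 4 labels the disease cohort as incident with an unlimited washout. That selects the first-ever diagnosis, and Table 5 lets it lie before observation, so the problem remains.

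**Historical dates may be few.** Section 11 concedes that not all GPs record such history as a matter of routine. This stands. The top of each range assumes complete recording with correct dates and is an upper bound under its model. For short survival the bias may be slight, and it vanishes if no prior diagnoses are recorded. The abstract, however, wants as much patient history as possible.

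**Opposite errors.** Section 11 notes that a first recorded diagnosis may postdate the real one, which shortens D. If unrecorded earlier diagnoses are instead first coded within two years of registration (an assumption), the 30-year case gives 1.19, 0.95 and 0.78 of the true median at 50%, 25% and 10% recorded. Delayed entry then gives 24.2, 22.1 and 21.0 years. So a reader should not infer that D is too long on balance in every disease, or that delayed entry repairs wrong dates.

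**Section 11 already warns.** It says wrong dates can bias the median duration. It does not name survival to entry as a condition of inclusion. Its remark that the comparison is unaffected follows the paediatric/adult misclassification point and offers no remedy. The diagnostics in section 10 look at age at diagnosis and survival among those who die, not at entry time.

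**Pre-2010 survival.** A reader might infer that including survival from before 2010 is itself an error, since incidence covers 2010–2022 only. The documents do not support that. The comparator is complete prevalence, which reflects earlier diagnosis years, and stable duration is a declared assumption in section 6.

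**Conclusion.** The point holds. As written, the survival analysis treats left-truncated data as fully followed, and this component of error in D is upward. Under the main set of assumptions, with 10% to 100% of historical diagnoses recorded, the inflation is about 1.02 to 1.3 times for true medians of 0.5 to 3 years and about 1.3 to 2.3 times for 15 to 30 years. Another plausible registration pattern gave larger factors at 3 and 10 years, so these are orders of size and not predictions for the three databases.

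A reader might infer that the indirect prevalence will exceed the direct one by the same factor. That does not follow: the factor applies relative to I × true median. Using the median for the mean, and late-recorded diagnoses, push the other way. The errors can nearly cancel (1.01 in the 5-year case), and in three of the five cases above correcting D alone moves I·D further from I × mean. That does not justify leaving the bias in. It means that agreement between the two prevalences could be accidental and disagreement could not be interpreted.

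**What to change.** In section 8.3, Table 4 and section 8.8.5, keep time since first diagnosis as the time scale and specify a left-truncated Kaplan-Meier, Surv(entry, exit, death):

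- Set entry to the later of first diagnosis and start of observation. If only patients present during the study period are included, set it to the latest of those two and 01/01/2010. State which cohort rule applies.
- Drop patients with no follow-up after entry.
- Report, by disease and database, the number diagnosed before entry and the numbers at risk over time.
- As a sensitivity analysis, limit D to diagnoses made during observation, under the same entry rule, where a median is reached. At a true median of 40 years it mostly was not, so it cannot replace the main analysis for long-lasting diseases.
- Name left truncation in section 11, separately from wrong dates, and say that the use of the median for the mean acts in the other direction.

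The cost is one changed call in the already planned *survival* package, plus wording. Early risk sets become smaller and the confidence interval for D wider, which carries through equation (5) into the indirect prevalence and the meta-analysis. In very small cohorts (section 8.8.1 allows analysis from 5 subjects) the truncated estimate can be unstable, so the numbers at risk should be shown next to each median.
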